20.	Subject Confidentiality	
21.	Termination of the Clinical Study	
22.	Insurance	
	II IOUI UI IOO	

Number	Revision / Date	Page
G02-CLP-0002_US	Rev. 08 / 27 July 2021	9 of 75

23.	Publication Policy	63
24.	Reporting Results on ClinicalTrials.gov	63
25.	Study Schedule	65
	,	
TAB	LE OF APPENDICES	
Apper	ndix 1 - BSW questionnaire	67
Apper	ndix 2 - MESA incontinence questionnaire	68
Apper	ndix 3 - OAB-q	70
	ndix 4 – PGI	
Vhhei	ndix 5 – PHQ-15	74
Apper	IIIIX 3 - FTQ-13	
Apper	ndix 6 – References	75

3. Acronym List

AE Adverse Event BL Baseline

BSW Benefit, Satisfaction and willingness to Continue questionnaire

CEC Clinical Event Committee
CIP Clinical Investigation Plan
CP Clinician Programmer
CRF Case Report Form

CTCAE Common Terminology Criteria for Adverse Events

DSMB Data Safety and Monitoring Board

FI Ethic Committee
Fi Fecal Incontinence
GCP Good Clinical Practice

HRQL Health Related Quality of Life IRB Institutional Review Boards

ITT Intend To Treat

MESA Medical, Epidemiological, and Social Aspects of Aging

MID Minimal Important Difference

MS Multiple Sclerosis
OAB Over Active Bladder

OAB-q Over Active Bladder questionnaire
OASIS Over Active bladder Stimulation System

PCB Printed Circuit Board

PPIUS Patient Perception of Intensity of Urgency Scale
PTNS Percutaneous/Posterior Tibial Nerve Stimulation
PGI-I Patient Global Impression of Improvement

PHQ-9 (or 15) Patient Health Questionnaire

PVR Post Void Residual
QoL Quality of Life
VD Voiding Diary

UADE Unanticipated adverse device effect

UUI Urinary Urge Incontinence

Number	Revision / Date	Page
G02-CLP-0002_US	Rev. 08 / 27 July 2021	11 of 75

4. Protocol Synopsis

FULL TITLE	A prospective study to assess the efficacy and safety of the BlueWind RENOVA iStim™ System in the treatment of patients diagnosed with overactive bladder (OASIS – OverActive bladder StImulation System study).	
RUNNING TITLE	BlueWind RENOVA iStim™ System for the treatment of OAB.	
STUDY INTENDED USE AND INDICATION FOR USE	The BlueWind Medical System is intended for peripheral nerve stimulation. The RENOVA iStim TM System is indicated for the treatment of women with symptoms of urgency incontinence alone or in combination with urinary urgency and/or urinary frequency.	
STUDY DESIGN	Prospective, interventional, multi-center, single arm, open label study.	
STUDY PURPOSE	To demonstrate efficacy and safety of BlueWind RENOVA iStim™ System therapy in the treatment of UUI.	

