13.5.7 Covariate Analyses

Covariate analyses will be done by comparing each endpoint between groups defined by the levels of the covariate at baseline, where continuous variables will be coded into two levels by median split. Analyses will be done by logistic regression. Covariates will include, but are not limited to:

- Age
- BMI
- OAB duration at baseline

Additionally, formal subgroup analyses will be conducted to assess the effects on the primary endpoint of antidepressant medications, and also to assess the potential impact of COVID-19 on the study outcomes. Details of these analyses are outlined in the SAP.

Finally, a test of homogeneity of effect across investigational center will be conducted. Descriptive statistics (e.g. success rate) will be reported for every participating center. Any center enrolling fewer than five subjects will be excluded from the formal test of homogeneity. To acknowledge that this test of homogeneity is fundamentally underpowered, a significance level of 0.15 will be used to determine whether a potential differential effect across centers exists and to trigger additional, exploratory analysis to better understand the nature of the difference.

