This endpoint is defined only for patients with baseline number of voids per day of at least 8 and baseline number of urgent episodes (PPIUS 3 or 4) of at least 9 per 7-day diary. It is expected that 70% of enrolled subjects will meet these criteria.

Sample size requirements to evaluate this secondary endpoint are calculated in the same manner as the primary, under the following assumptions:

- Significance level = 0.025 (one-sided)
- Power ≥ 85%
- Assumed treatment success rate at 6 months = 61%
- Prespecified performance goal = 45%

A total of 89 evaluable subjects are required. Assuming 15% attrition rate, a total of 105 subjects meeting the criteria described above is needed. With 70% of enrolled subjects meeting the analysis criteria, 150 total sample size is sufficient to evaluate the secondary endpoint.

The total sample size for the OASIS trial is 150 subjects.

10 Data Derivation and Transformation

Data not specifically recorded on a CRF will be derived as follows:

- Study Duration [days] = Date of Last Visit Date of First Visit + 1.
- HbA1c values will be reported in units of mmol/mol. For cases of HbA1c reported in percentage, the following conversion formula will be used:

Document ID	Revision / Date	Page
G02-CLP-0009	Rev. 06 / 18 May 2022	16 of 26

HbA1c (mmol/mol) = $[HbA1c (\%) - 2.15] \times 10.929^{1}$

- Coding of Adverse Events will be done using the most recent MedDRA version.
- Coding of Concomitant Medication will be done using the most recent WHO Drug dictionary version.
- Baseline will be defined as the value at the "Enrollment and Screening" visit unless noted otherwise.
- OAB duration at baseline from Date of OAB Diagnosis [years] = Date of Screening Date of OAB Diagnosis/365.25.
- Partial dates that are required for analysis will be imputed in the following fashion:
 - o Dates with missing month and day will be imputed as July 1st.
 - o Dates with missing day only will be imputed as the 15th of the month.
- Since querying of paper diaries is not possible at the time of completion and not feasible in an accurate
 manner afterwards, no query management process is used for the paper diaries. In its place a set of
 automatic rules will be applied to correct discrepancies in the paper diaries, as detailed in the appendix
 to the SAP.

11 Interim Analysis

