12.8 Covariate, Subgroup, and 'Poolability' Analyses

Covariate analyses will be done by comparing the primary endpoint by the levels of the covariate at baseline, where continuous variables will be coded into two levels by median split. Analyses will be done by logistic regression. Covariates will include, but are not limited to:

- Age
- BMI
- OAB duration at baseline
- US vs. Outside of US (OUS)
- Race and ethnicity
- Baseline average urgency leaks/day
- Baseline average voids/day
- Smoking history (Past/Current/Never)
- Concomitant OAB medication at time of screening
- Ratio between average stress related leaks and average urgency related leaks at baseline.

For each of the listed above covariates descriptive statistics of the primary endpoint by covariate levels will be

Document ID	Revision / Date	Page
G02-CLP-0009	Rev. 06 / 18 May 2022	23 of 26

presented. Continuous covariates will be divided into quartiles for this presentation. Additionally, formal subgroup analyses will be conducted to assess the effects on the primary endpoint of antidepressant medications and OAB medication, and also to assess the potential impact of COVID-19 on the study outcomes.

The analyses for antidepressant medications and OAB medications will be structurally similar. The first level of the analyses for each medication type will compare treatment effect (success rates) among those taking and not taking the respective medication at baseline. This will be performed as a logistic regression model, with baseline status as an indicator variable. If there is no difference in outcome, the second level of the analysis will be a logistic regression analysis on all subjects, with an indicator variable for changes in medication (lower, same or higher total dosage). If there is a differential effect concerning baseline status, the second level analysis will be comprised of two analyses; one only consisting of the subjects on the respective medication at baseline, with an indicator for any subsequent changes, and this will be repeated for the complementary subgroup of those subjects not on the respective medication at baseline. For each level of analysis, the success rate for each level of the subgroup will be reported for completeness. It should be noted that changes in usage of antidepressants and OAB medications will need to be defined and filtered from the concomitant medications form in exploratory fashion.

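### The supportive covariate models split continuous baseline covariates at the median, which weakens the search for baseline predictors of response; a minor, nearly free improvement

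*SAP*

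**What the plan says.** SAP 12.8 compares the primary endpoint across levels of each baseline covariate. Its coding rule is that "continuous variables will be coded into two levels by median split", and its method is stated as "Analyses will be done by logistic regression". Ten covariates are listed, and the list is left open. Six are continuous: age, BMI, OAB duration, baseline urgency leaks per day, baseline voids per day, and the ratio of stress to urgency leaks.

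Protocol 13.5.7 has the same coding rule ("where continuous variables will be coded into two levels by median split") but a wider scope: "Covariate analyses will be done by comparing each endpoint between groups defined by the levels of the covariate at baseline". It names age, BMI and OAB duration, all continuous.

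SAP 12.8 also plans a descriptive table of the primary endpoint by covariate level, for which it says: "Continuous covariates will be divided into quartiles for this presentation".

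The design in the protocol synopsis is "Prospective, interventional, multi-center, single arm, open label study". SAP section 9 states: "The total sample size for the OASIS trial is 150 subjects". Neither document gives a hypothesis, power target or significance level for the covariate models.

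**The concern.** A median split treats the youngest and the nearly median-aged subject as the same, and treats two subjects just either side of the median as different. The cut point depends on the sample and has no clinical meaning. If response changes gradually with the covariate, the model discards most of what it could use to see that change.

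Protocol 13.5.1 gives covariate assessment a purpose: to judge how widely the results apply. With 150 subjects, power for such questions is limited from the start. The documents accept this for the centre comparison, where they relax the significance level to 0.15 because the test is underpowered. For the continuous covariates they make no such allowance, and the coding rule lowers power further.

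The COVID-19 model in SAP 12.8 is covariate-adjusted in the manner described earlier in that section. Read literally, it would inherit the split covariates, so its adjustment would be coarser too.

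**Working it through.** **1. The plan's own figures.** No power or sample size is stated for the covariate models, so the nearest figures are those of SAP section 9 and protocol 13.4 (exact one-sided binomial test, α = 0.025).

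- Primary endpoint, 65% against 50%: N = 114 with at least 68 responders gives α = 0.0244 and power 90.2%. 114/0.85 = 134.1; the plan has 134.
- Secondary endpoint, 61% against 45%: N = 89 with at least 50 responders gives α = 0.0223 and power 85.1%. 89/0.85 = 104.7, so 105; 105/0.70 = 150.

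These reproduce. (SAP section 9 gives the primary power as at least 80% where the protocol gives at least 90%. That is a separate matter and does not affect this point.) The covariate models therefore have 150 subjects, or about 127 observed outcomes after 15% attrition (150 × 0.85 = 127.5).

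**2. Information kept by a median split.** For a small linear effect, the efficiency of the split relative to a linear term is the squared correlation between the covariate X and the high/low indicator I:

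efficiency = cov(X, I)² / [var(X) · var(I)], with var(I) = 1/4.

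- Normal: cov = 1/√(2π), so efficiency = (1/2π)/(1/4) = 2/π = 0.637. Then 150 subjects act like 150 × 0.637 ≈ 95, and 127 like 81.
- Uniform on 0 to 1: cov = 3/8 − 1/4 = 1/8, so efficiency = (1/64)/(1/48) = 0.75, a loss of 25%.
- Exponential: cov = (ln 2)/2, so efficiency = (ln 2)² = 0.48, a loss of 52%.
- By simulation (2,000,000 draws): gamma with shape 3 to 10, 0.58 to 0.62; lognormal with log-SD 0.5, 0.75 and 1.0, 0.52, 0.40 and 0.27.

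The covariate shapes are assumptions; the documents give none.

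**3. Power.** Assumptions, none of them in the documents for these models: normal covariate, effect linear in the log-odds, overall response 65%, two-sided 0.05 likelihood-ratio test. There were 8,000 simulated trials per setting, so the simulation standard error is at most √(0.25/8000) = 0.6 points.

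| Odds ratio per SD | N=150 continuous | N=150 split | N=127 continuous | N=127 split |
|---|---|---|---|---|
| 1.0 (no effect) | 5.2% | 5.1% | 5.2% | 5.2% |
| 1.3 | 33.0% | 22.9% | 29.5% | 20.7% |
| 1.5 | 64.3% | 45.7% | 57.2% | 40.7% |
| 1.75 | 88.2% | 70.4% | 82.6% | 64.2% |
| 2.0 | 96.7% | 86.2% | 94.0% | 80.4% |

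Both codings hold the error rate. The gap at N = 150 runs from 10.1 points (odds ratio 1.3) to 18.6 (1.5), and is 10.5 at 2.0. Separate runs at a log-odds of 0.4 per SD (odds ratio e^0.4 = 1.49) gave 63% against 44 to 45%, in line with the 1.5 row.

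With a lognormal covariate (log-SD 0.75) and an effect linear on its own scale, N = 150 gives 51.7% against 27.9% at an odds ratio of 1.5.

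**4. A case where the split wins.** If response is 55% below the median and 75% above it, the split is the stronger test: 68.2% against 54.7% at N = 150, and 60.4% against 47.9% at N = 127.

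**5. Scale matters.** A split is unaffected by a log transformation; a linear term is not. Suppose X is lognormal with log-SD σ and the effect is linear in log X. The split then keeps 2/π = 0.64. An untransformed linear term keeps σ²/(e^{σ²} − 1), which at σ = 1 is 1/(e − 1) = 0.58. For a strongly skewed covariate the gain therefore depends on using a suitable scale, which is why the fix includes a transformation.

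**The case against.** **Nothing decisive rests on these models.** This stands. The primary success rule (SAP 12.6.1) and the secondary rules (SAP 12.6.2) do not use them. A reader might infer that the split reaches the primary result, because that too is tested by logistic regression after imputation. The documents do not support this: SAP 12.6.1 names no covariate in the test model, and SAP 7.1 lists the imputation covariates without any split.

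**The quartile table already shows gradients.** This stands in part. A trend across quartiles would be visible, so a gradient need not go unseen. But the table is descriptive and restores no power to the model. A reader might also infer that a non-significant covariate test will be reported as proof of a consistent response; neither document says so.

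**The size rests on assumptions, and the direction can reverse.** This stands as a limit on the figures. The odds ratios, covariate shapes and two-sided 0.05 level are all assumed. A step at the median favours the split, but the true threshold would have to lie at or near this sample's median, and the documents give no reason to expect that.

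**A linear term can be driven by a few extreme values.** This is fair. Entry requires at least nine urgency leaks in seven days, which cuts off the low end of baseline leaks, and OAB duration and the stress-to-urgency ratio may also be right-skewed (an assumption). It is an argument for transformation and a curvature check rather than for a split.

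**Conclusion.** The point holds as a minor improvement. The split keeps 64% of the information for a roughly normal covariate with a log-odds-linear effect. A loss of about a third should not be read as general: under other assumed shapes it runs from about 25% (uniform) to over 50% (strongly right-skewed). Under the stated assumptions the cost in power at N = 150 is about 10 to 19 points for odds ratios of 1.3 to 2.0 per SD. Among the settings simulated with a real effect, the split was stronger only where response stepped at the median.

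A reader might infer that the trial's ability to find effect modifiers is at stake. The design does not support that: with no control arm, no treatment-by-covariate interaction can be estimated. SAP 12.8 itself equates effect with response in its medication analyses, which "compare treatment effect (success rates) among those taking and not taking the respective medication at baseline". What is weakened is the search for baseline predictors of response.

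**What to change.** Change SAP 12.8 and protocol 13.5.7 together, or record a departure from the protocol, before database lock:

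- Enter each continuous covariate in its logistic model as a continuous term, log-transformed where right-skewed. Name the transformed covariates before outcomes are examined. If the stress-to-urgency ratio can be zero, use the log of one plus the ratio.
- Prespecify a quadratic or spline term to check curvature, and report it if it improves the fit.
- Give the odds ratio per SD or per stated unit, with its confidence interval.
- Keep the quartiles for display only.
- Use the same coding in the COVID-19 model.
- While editing, settle whether the covariate models cover every endpoint (protocol) or only the primary endpoint (SAP).

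The cost is a small text edit in both documents and reporting slightly less simple than a high/low comparison. No extra subjects, visits or data are needed.

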8.4 Additional Efficacy Endpoints

The following additional efficacy endpoints will be assessed based on the data summarized in the data management reports:

- Patient Global Impression of Improvement (PGI-I) score
- Treatment Benefit, Satisfaction, and Willingness to Continue (BSW)
- Improvement in OABq (HRQL (and its subscales) and symptoms severity)
- Changes in the following OAB symptoms as measured by voiding diary 6 and 12-months post system activation compared to baseline:
 - o Reduction in the average number of severe/large urgency related incontinence episodes
 - o Reduction in the number of micturition episodes.
 - o Reduction in the number of urgency related incontinence episodes.
 - Reduction in degree of urgency prior to void on Patient Perception of Intensity of Urgency Scale (PPIUS) from 0-4.
 - o Reduction in severity of incontinence episodes (amount leaked).
- Proportion of dry subjects following treatment with the RENOVA iStim System as measured by 3
 consecutive days of a patient voiding diary.
- Assessment of fecal incontinence symptoms in patients suffering from mixed fecal and urine incontinence.
- Device usage
- Patient compliance with treatment through 6-months

Instructions for Diary calculation are as detailed in the appendix to the SAP.

9 Sample Size Considerations

The sample size for the primary endpoint was calculated using PASS 2015 software by a one-sided exact test for a single binomial population, under the following assumptions:

Document ID	Revision / Date	Page
G02-CLP-0009	Rev. 06 / 18 May 2022	15 of 26

- Significance level = 0.025 (one-sided)
- Power ≥ 80%
- Assumed treatment success rate at 6 months = 65%
- Prespecified performance goal = 50%.

Given these assumptions, 114 evaluable subjects are required. A total of 134 enrolled subjects, accounting for 15% attrition, is sufficient to evaluate the primary endpoint. However, this sample size is not adequate to evaluate all secondary objectives with sufficient power – specifically the following important secondary objective:

To demonstrate the proportion of responders at 6 months post system activation, defined by ≥50% improvement in the average number of moderate-severe urgency episodes PPIUS degree 3,4 or <8 voids/day, is greater than 45%.

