Any subjects enrolled prior to the COVID-19 outbreak may be subject to telephone follow-ups instead of onsite follow-up visits for a period of time. Interactions with affected subjects, then, would be different than for those who are routinely followed in the clinic, and only a subset of data will be able to be collected. A covariate adjusted logistic regression model, as described above, will be fit to assess the potential impact of COVID-19 on study outcomes, with an indicator variable indicating subjects enrolled prior to, and after, stay- at-home policies were enacted.

Finally, a test of homogeneity of effect across investigational center will be conducted. Descriptive statistics (e.g. success rate) will be reported for every participating center. Any center enrolling fewer than five subjects will be excluded from the formal test of homogeneity. To acknowledge that this test of homogeneity is fundamentally underpowered, a significance level of 0.15 will be used to determine whether a potential differential effect across centers exists and to trigger additional, exploratory analysis to better understand the nature of the difference.

13 Long-Term Follow-Up

Upon completion of the 12-month follow-up visits, patients will enter a long-term follow-up phase. Formal study visits will occur at 24 and 36 months. Less comprehensive visits conducted via telephone will be conducted at months 18 and 30. The telephone visits will assess adverse events and subject diary data.

Document ID	Revision / Date	Page
G02-CLP-0009	Rev. 06 / 18 May 2022	24 of 26

All primary, secondary and additional efficacy measures will be summarized using appropriate descriptive statistics - mean, median, standard deviation and 95% confidence intervals for continuous measures and frequency distributions for categorical or binary data. Adverse events, and treatment regimen data will be summarized.

14 Data Listings

Data listings will be provided for all data available from the CRF.

15 Computer Software

All statistical analyses will be carried out using SAS® Version 9.4 or higher under Windows® 2016 Terminal.

Document ID	Revision / Date	Page
G02-CLP-0009	Rev. 06 / 18 May 2022	25 of 26

16 Appendix 1: Rules for Correction of Discrepancies in Paper Diaries

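### SAP 12.8 lets an undefined finding of no difference between baseline medication users and non-users choose the second-level model, although that comparison cannot show that pooling is safe

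*SAP*

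**What the plan says.** SAP 12.8 plans a two-level analysis of the primary endpoint, built the same way for antidepressants and for OAB medication.

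- **Level 1.** "The first level of the analyses for each medication type will compare treatment effect (success rates) among those taking and not taking" the medication at baseline. "This will be performed as a logistic regression model, with baseline status as an indicator variable".
- **Level 2 when no difference is seen.** "If there is no difference in outcome, the second level of the analysis will be a logistic regression analysis on all subjects". The only term named is an indicator for change in medication (lower, same or higher total dosage).
- **Level 2 when a difference is seen.** "If there is a differential effect concerning baseline status, the second level analysis will be comprised of two analyses", one in baseline users and one in non-users.

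The section gives no significance level, interval rule or margin for deciding between the branches, no expected share of users and no power. It does say that success rates for each subgroup level will be reported at each level of analysis, and that medication changes will be defined in an exploratory way. For the centre test, the same section is explicit: "To acknowledge that this test of homogeneity is fundamentally underpowered, a significance level of 0.15 will be used".

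**The concern.** The choice of second-level model rests on a pre-test whose criterion is not stated and whose null result is read as equality. Pooling also drops baseline use from the named terms, so the medication-change estimate then mixes subjects who differ in what a change can mean.

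This matters because the trial is single-arm and open-label and medication can change during follow-up. Protocol 10.4.2 has medically required changes to OAB, diuretic or antidepressant medication recorded, with the patient continuing as planned. The rule that counts a significant increase in UUI medication as failure sits under missing-data handling (SAP 7.1, Protocol 13.2.1). Section 12.8 is the only place found in the SAP that sets medication change against the primary endpoint; its covariate list covers OAB medication only at screening. An effect of change confined to baseline users could be blurred in the pooled model.

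**Working it through.** **1. What the gate tests against what pooling needs.** Let U be baseline users, N non-users, k the change category, w the share of a group in category k, and p its success rate.

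- Level 1 tests p_U = p_N, where p_U = Σ w_Uk p_Uk and p_N = Σ w_Nk p_Nk.
- Pooling the change effect needs p_U,higher − p_U,same = p_N,higher − p_N,same.

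The first equality concerns two weighted averages and the second concerns contrasts within groups. Neither implies the other, at any sample size.

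The pooled categories have these contents:

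| Category | Baseline users | Baseline non-users |
|---|---|---|
| Lower | dose reduced or stopped | cannot occur |
| Same | stable users | never-users |
| Higher | dose increased | newly started |

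So lower against same compares users only with a mixture of users and non-users. Higher against same mixes dose increases with new starts.

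**2. Inputs for power.** The plan states no power for this test, so there is no figure for it to reproduce.

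- From SAP section 9: N = 150 ("The total sample size for the OASIS trial is 150 subjects"), a 65% success rate, a 50% performance goal and 15% attrition. As a check on those inputs, the primary sizing reproduces: n = 114 with at least 68 responders gives exact one-sided alpha 0.0244 and power 90.2%.
- Assumed, because the documents do not say: two-sided 0.05 at level 1; user share s of 10, 20, 30 or 50%; overall success held at 65%; users doing worse by d.

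**3. Formula.** p_U = 0.65 − d(1 − s), p_N = 0.65 + d·s, n_U = 150s, n_N = 150 − n_U.

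Power = Φ[(d − 1.96·SE0)/SE1], with SE0 = √{0.65 × 0.35 × (1/n_U + 1/n_N)} and SE1 = √{p_U(1 − p_U)/n_U + p_N(1 − p_N)/n_N}.

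**4. Worked case, s = 20%, d = 15 points.** n = 30 and 120; p_U = 0.65 − 0.12 = 0.53; p_N = 0.65 + 0.03 = 0.68; SE0 = 0.0974; SE1 = 0.1006. Power = Φ[(0.15 − 0.1908)/0.1006] = Φ(−0.41) = 34%.

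**5. Results, N = 150, two-sided 0.05.**

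| True difference | 50% users | 30% | 20% | 10% |
|---|---|---|---|---|
| 10 points | 25% | 22% | 18% | 13% |
| 15 points | 49% | 42% | 34% | 22% |
| 20 points | 73% | 65% | 54% | 34% |
| 25 points | 90% | 83% | 72% | 49% |

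The difference detected with 80% power is 21.7, 24.0, 27.5 and 36.2 points respectively. Full enumeration of the logistic Wald and likelihood-ratio tests agrees within 2 points. Using SE1 in place of SE0 moves the entries by at most about 3 points: 11–25% for 10 points and 20–50% for 15 points across all shares, and 51–91% for 20–25 points at 20–50% users.

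**6. Sensitivity.** With 150 × 0.85 ≈ 128 observed, power is 43/37/30/20% for 15 points and 66/58/48/31% for 20 points. At the 0.15 level that the SAP sets for centres, with N = 150, it is 44/40/34/26% for 10 points, 69/62/54/39% for 15 and 88/81/72/54% for 20.

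**The case against.** The strongest reply is that this is a secondary, largely exploratory analysis and that much of the remedy is already present. User and non-user success rates are reported whichever branch is taken. OAB medication at screening is also a listed covariate. Subjects on OAB drugs must be on a stable dose for 3 months before baseline and agree to stay stable to 12 months (Protocol 10.4), which suggests few changes. All of that stands and keeps the point small. It does not supply confidence intervals, and in the pooled branch it does not promise rates by change within baseline use.

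Four stronger readings are tempting and are not supported.

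- **That the first test will usually miss any real difference.** At 20–50% users it finds 20 points 54–73% of the time and 25 points 72–90%. The documents give neither the share of users nor a plausible difference.
- **That non-significance at 0.05 is the stated gate.** The SAP states no criterion. At 0.15, power for 15 points reaches 54–69% with 20–50% users.
- **That the power figures measure how often a dose-change effect is hidden.** They concern the main effect of baseline use. The loss on the interaction is not quantified here.
- **That pooling touches the main result, or that medication is the leading rival explanation.** The success rule in SAP 12.6.1 does not use this branch. The documents do not rank medication in that way; Protocol 5.2 names the placebo effect.

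It is also fair that a joint model will have sparse cells, and one cell that is empty by construction.

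**Conclusion.** The concern holds in a limited form. The decisive defect needs no power assumption: equal overall success in users and non-users does not show that a medication change acts alike in both, so the gate cannot license pooling, and its criterion is undefined. Low power adds to this for moderate differences. It is 13–25% for 10 points and 22–49% for 15 points, and 15 points equals the gap between the assumed 65% and the 50% goal. Those figures rest on a two-sided 0.05 test, 10–50% users, an overall rate of 65% and 150 analysed subjects. The effect is confined to the second-level medication-change models. The primary analysis and its success rule are unchanged, and the point is minor.

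**What to change.** Remove the branch from SAP 12.8. For each medication type:

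- Keep the level 1 comparison as a description, and report the user minus non-user difference with its confidence interval.
- Whatever level 1 shows, fit one prespecified second-level logistic model that always includes baseline use and medication change.
- Always tabulate success rates with confidence intervals by baseline use and change: lower, same and higher for users; same and higher for non-users, stating that lower does not exist for them.
- Treat any interaction between baseline use and change as descriptive. The main-effects model assumes a common effect of change, and the table lets the reader judge that assumption.

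Stating a threshold for the gate, even 0.15, would define the rule and raise power, but it would still test the wrong quantity.

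The cost is SAP wording and a few table shells, with no new data. The downside is that some cells will be sparse and their intervals wide.
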